**Figure 2 Study Sequence: Part 2 Multiple Ascending Doses**

## 8.2 Criteria for In-Study Decisions

In-study decisions will be made by the safety advisory committee (SAC) which will always comprise the Sponsor, investigator (or delegate), the Sponsor's representative medical monitor (or delegate) and a PK expert, where PK expertise is required.

### 8.2.1 Decision Points

For all cohorts where a sentinel dosing strategy is utilized, the decision to proceed with dosing of the main group will be made by the investigator based on safety data through 72 hours post-dose of the sentinel subjects. The investigator will inform the Sponsor of any safety concerns.

The following in-study decisions will be made by the SAC during this study:

- Whether to progress to the next dose level
- Dose level selection for each SAD and MAD regimen
- After at least SAD Cohort 3 has been dosed: whether to progress to MAD Part 2 of the study
- When progressing to MAD Part 2 of the study, whether a loading dose is required and the amount of the loading dose: loading doses will be chosen based on PK/PD (if available) and safety data and will not exceed the highest dose given in the SAD study
- After MAD Cohorts 1 to 3: whether optional MAD Cohort 4 is required
- Changes to safety and/or PK and/or PD time points if there is reason to believe that the change might improve the quality of the data based on review of emerging data. These changes may also be implemented by the Sponsor alone.

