Based on the maximum allowed escalations and anticipated PD activity, the highest anticipated dose will be 12600 µg. Using the NOAEL of 18 mg/kg in monkeys, the HED-based safety factor is approximately 32. With the predicted human PK at 12600 µg (assuming 70kg patients and 90% SC bioavailability), the dose-based, concentration (Cmax)-based, and exposure (AUC)-based safety factors are estimated to be 100, 231, and 24, respectively.

Doses administered will be predicted not to exceed a mean Cmax of 103,950 ng/mL and a mean AUC(0-24h) of 1,775,000 ng.h/mL, which is the sex-averaged mean NOAEL exposure limits after the first dose of 18 mg/kg in the cynomolgus NOAEL 28-day good laboratory practice (GLP) toxicology study, in any individual subject.

The non-clinical program, containing pharmacology, PK, PD, and toxicology data of PDM608, supports the initiation of a human clinical study for the treatment of neurodegenerative diseases.

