## 8 Study Design

### 8.1 Study Plan

This is a 2-part, single-center, first-in-human study of SAD (Part 1) and MAD (Part 2) doses of PDM608 in healthy adult subjects. The 2 parts are not required to be conducted entirely sequentially provided that this is justified by safety data obtained from completed cohorts. The first MAD cohort will not be dosed until a minimum 3 SAD cohorts have undergone review by the SAC, and dosing for each MAD cohort will be at a dose level 2-3 fold lower than the highest SAD cohort dose deemed safe by the SAC at the time of each MAD cohort initiation.

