#### 8.1.1 Study Plan: Part 1 Single Ascending Doses

Part 1 is a double-blind, randomized, placebo-controlled assessment of SC PDM608 SAD administrations. Subjects will be enrolled sequentially into 1 of up to 5 cohorts, each containing 8 subjects. Within each cohort, 6 subjects will be randomly assigned to receive PDM608 and 2 subjects will be randomly assigned to receive matching placebo. An evaluable subject for Part 1 is defined as a subject who has received the IMP dose and undergone all safety and tolerability assessments (inclusive of all scheduled hematology assessments) out to 96 hours post.

All SAD Cohorts will follow a sentinel design. On the first day of dosing only 2 (sentinel) subjects will be dosed. The randomization schedule will be constructed such that 1 of the subjects dosed on the first day will receive PDM608 and 1 will receive placebo. After review of the safety data from the 72 hours post-dose period the Investigator will decide whether to proceed with dosing the remaining subjects in the cohort (main group; 5 subjects randomized to receive PDM608 and 1 subject randomized to receive placebo).

Following completion of each cohort the safety and tolerability assessments through 96 hours post-dose (Day 5) will be reviewed by the SAC to determine whether to progress to the next dose level and the dose level for the next cohort, with a maximum 3-fold increase in dose level between SAD cohorts.

Following dosing of at least 3 SAD cohorts, the SAC will also decide whether to progress to MAD Part 2 of the study and, if so, on the starting dose for the first MAD cohort. Part 2 may be dosed in parallel with Part 1, but the decision to proceed to Part 2 can only be made following interim review of safety and tolerability data from doses through SAD Cohort 3. Full details of the interim data reviews are provided in [Section 8.2](#).

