**Figure 1 Study Sequence: Part 1 Single Ascending Doses****8.1.2 Study Plan: Part 2 Multiple Ascending Doses**

Part 2 is a double-blind, randomized, placebo-controlled assessment of SC PDM608 MAD administrations. Subjects will be enrolled sequentially into 1 of up to 4 cohorts, each containing 12 subjects. Within each cohort, 9 subjects will be randomly assigned to receive PDM608 and 3 subjects will be randomly assigned to receive matching placebo. MAD Cohort 4 is optional; the decision on whether to dose this cohort will be based on interim review of preceding MAD Cohorts 1 to 3.

Part 2 may be dosed in parallel with Part 1, but can only proceed following interim review of safety and tolerability data from at least the first 3 SAD cohorts in Part 1. Dosing for each MAD cohort will be at a dose level 2-3 fold lower than the highest SAD cohort dose deemed safe by the SAC at the time of each MAD cohort initiation.

An evaluable subject for Part 2 is defined as a subject who has received all 4 doses of IMP and undergone all safety and tolerability assessments out to 96 hours post-final dose (dose 4). Sentinel dosing is not planned for MAD cohorts, but the SAC may implement a sentinel design if deemed appropriate.

Following completion of each cohort, the safety and tolerability assessments out to 96 hours post-final dose (Day 26) will be reviewed to determine whether to progress to the next dose level and the dose to be administered. Full details of the interim data reviews are provided in [Section 8.2](#).

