### 8.2.2 Criteria for Dose Decision

Progression to the next dose group will be permitted after review of defined safety and tolerability data suggests that it is safe to do so. All SAC decisions will be documented and signed by the investigator and Sponsor medical monitor or delegate. Evidence of the decision will be retained in the Trial Master File (TMF).

For dose escalation in the SAD phase to proceed data must be available from a minimum of 6 subjects who have completed the planned safety and tolerability assessments out to 96 hours post-dose (Day 5), to ensure at least 4 subjects receive active IMP. For dose escalation in the MAD phase to proceed data must be available from a minimum of 8 subjects who have completed the planned safety and tolerability assessments out to 96 hours post-final dose (Day 26) to ensure at least 6 subjects receive active IMP.

It is planned that the dose will be escalated for each subsequent cohort; however, the SAC may also agree to enroll additional subjects for an intermediate dose level if warranted or may agree to reduce the dose with no limit on the possible extent of reduction. Any decision to investigate an intermediate or reduced dose level will be fully documented.

The decision to proceed to the next dose level will be based on safety and tolerability and data. The following data are required:

- AEs
- Vital signs
- Safety laboratory, including review of PD hematology parameters outlined in [Section 6.4](#)

- 12-lead ECG
- Physical examinations

The SAC may also consider additional data as it becomes available and as relevant to decisions, including ADA, PD, and PK.

Rules for dose decision are as follows:

- Dose escalation will not be more than 3-fold between SAD cohorts. Anticipated SAD dose levels are described in [Table 2](#).
- Dose escalation will not be more than 3-fold between MAD cohorts.
- Dosing for each MAD cohort will be at a dose level 2-3 fold lower than the highest SAD cohort dose deemed safe by the SAC at the time of each MAD cohort initiation.
- Doses administered will be predicted not to exceed a mean  $C_{max}$  of 103,950 ng/mL and a mean  $AUC_{(0-24h)}$  of 1,775,000 ng.h/mL, which is the sex-averaged mean NOAEL exposure limits after the first dose of 18 mg/kg in the cynomolgus NOAEL 28-day good laboratory practice (GLP) toxicology study, in any individual subject.

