- The predicted mean steady state exposures in the MAD ( $C_{max}$  and  $AUC$ ) factoring the potential for accumulation will not be anticipated to exceed mean maximal exposures observed in the SAD that were confirmed to be safe and well tolerated.
- The maximum PDM608 dose administered in either part of this trial will not exceed a dose that is more than two-fold above the dose at which any two of the following three pharmacodynamic activities are observed in a sample that includes a minimum 5 of 6 PDM608-treated subjects in SAD or 7 of 9 PDM608-treated subjects in MAD, treated within the same cohort, and observed at any laboratory timepoint up to and including 96 hours post-dose (SAD) and post-final dose (MAD):
  - An increase in mean WBC from pre-dose baseline by  $\geq 3$ -fold
  - An increase in mean monocytes from pre-dose baseline by  $\geq 2$ -fold
  - An increase in mean eosinophils from pre-dose baseline by  $\geq 7$ -fold
- The study will be halted and further dose decisions will be paused:
  - One or more subjects experience a possibly IMP-related serious adverse event (SAE)
  - Two or more subjects experience a possibly IMP-related non-serious AE of severe severity in one cohort in the same organ system class

The decision to reinitiate dosing will be made by the Sponsor in consultation with the investigator after review of safety data and notification to the Institutional Review Board (IRB).

If, following review by the SAC, it is deemed acceptable to continue dose escalation above a defined exposure limit, a substantial amendment with relevant data will be submitted for approval to the regulatory authorities and IRB.

---

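### The MAD loading-dose ceiling refers to the highest SAD dose given, not the highest cleared by the SAC, so it can sit 2- to 3-fold above the highest cleared dose

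*Combined protocol and SAP*

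**What the plan says.** Section 8.2.1 lists, among the SAC's decisions on moving to Part 2, whether a loading dose is needed and how large it should be. The choice rests on safety data and on PK/PD if available, and the dose "will not exceed the highest dose given in the SAD study". Section 8.2.2, which sets out the dose rules, does not mention loading doses.

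Two rules in Section 8.2.2 tie MAD dosing to SAD results, and both require clearance:

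- Weekly dose: "Dosing for each MAD cohort will be at a dose level 2-3 fold lower than the highest SAD cohort dose deemed safe" by the SAC when that cohort starts. Sections 8.1 and 8.1.2 repeat this.
- Predicted steady-state exposure: it must stay within "mean maximal exposures observed in the SAD that were confirmed to be safe and well tolerated".

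On timing, Section 8.1 states: "The 2 parts are not required to be conducted entirely sequentially". MAD dosing may begin once the SAC has reviewed at least three SAD cohorts. In each SAD cohort, Section 8.1.1 says: "On the first day of dosing only 2 (sentinel) subjects will be dosed". One of these two subjects receives active drug, and the remaining six wait for the 72-hour sentinel review. For SAD escalation, Section 8.2.2 says "data must be available from a minimum of 6 subjects who have completed the planned safety and tolerability assessments out to 96 hours post-dose", so that at least 4 have received active drug. Section 8.1.2 adds: "Sentinel dosing is not planned for MAD cohorts", although the SAC may introduce it.

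**The concern.** A dose becomes *given* when the first subject receives it. It becomes *deemed safe* only after the SAC has seen the cohort's data. The loading dose would be the largest single dose a MAD subject receives, yet its ceiling is tied to the earlier and weaker of these two events.

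The two can differ in two ways:

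1. **Overlap.** A higher SAD cohort may be under way, but not reviewed, when the MAD loading dose is set.
2. **Declined dose.** The SAC may review the top SAD dose and not clear it. That dose stays the highest given, so the ceiling never falls. This needs no overlap.

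In the SAD part a new dose level goes first to one active subject, followed by a 72-hour hold. In a MAD cohort without sentinels, a loading dose could reach up to 9 active subjects without that step. This is a first-in-human study, and Section 6.5 names excessive GM-CSF pharmacology as a major risk.

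**Working it through.** **Inputs**

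- Anticipated SAD doses (Table 2): 350, 1050, 3150, 6300 and 12600 µg.
- Maximum SAD step (Section 8.2.2): 3-fold.
- Weekly MAD dose (Section 8.2.2): between C/3 and C/2, where C is the highest cleared SAD dose.
- Sentinel hold (Section 8.1.1): 72 h. Follow-up needed for SAC review (Section 8.2.2): 96 h, in at least 6 subjects.
- Safety factors at 12600 µg (Section 6.2).

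**Check on the plan's own figures.** The anticipated steps are 1050/350 = 3, 3150/1050 = 3, 6300/3150 = 2 and 12600/6300 = 2, all within the 3-fold limit. The dose-based factor at 12600 µg is 18 mg/kg ÷ (12.6 mg/70 kg) = 18/0.18 = 100, as stated. The Cmax and AUC factors (231 and 24) rest on predicted human PK and are taken as given.

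**Step 1: how long a dose is given but not reviewable.** The sentinel pair supplies only 2 of the 6 subjects needed, so main-group data are required. The main group cannot start before 72 h and then needs 96 h of follow-up: 72 + 96 = 168 h, or 7 days after the first sentinel dose, at the earliest.

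**Step 2: size of the gap.** Let G be the highest dose given.

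| C (µg) | G (µg) | G/C | Weekly dose, C/3 to C/2 (µg) | Written ceiling ÷ weekly dose | Ceiling at C ÷ weekly dose |
|---|---|---|---|---|---|
| 3150 | 6300 | 2 | 1050–1575 | 6300/1575 = 4 to 6300/1050 = 6 | 2 to 3 |
| 6300 | 12600 | 2 | 2100–3150 | 12600/3150 = 4 to 12600/2100 = 6 | 2 to 3 |
| 3150 | 9450 (3 × 3150) | 3 | 1050–1575 | 9450/1575 = 6 to 9450/1050 = 9 | 2 to 3 |

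The excess due to the wording is the G/C column, 2-fold and up to 3-fold. The rest of the multiple over the weekly dose is the 2- to 3-fold ratio that remains available at a cleared dose.

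**Step 3: whether another written limit closes the gap.**

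- *NOAEL exposure limits (Sections 6.2 and 8.2.2).* At 12600 µg the dose-, Cmax- and AUC-based "safety factors are estimated to be 100, 231, and 24, respectively". These limits are far from binding at any planned dose.
- *PD cap (Sections 6.4 and 8.2.2).* It applies in both parts, but only after two of three hematology criteria are met, and it then allows up to twice the triggering dose. If triggered at C = 3150 it still admits 2 × 3150 = 6300 µg; at C = 6300 it admits 12600 µg. It would exclude 9450 µg if triggered at 3150 µg.
- *Steady-state rule (Section 8.2.2).* It concerns predicted steady state and does not expressly cover the peak after a loading dose.
- *Halt and stopping rules (Sections 8.2.2 and 8.5).* They act on a related SAE, two related severe AEs in one cohort and organ class, or liver injury. They do not act on a dose that is merely unreviewed, or declined for lesser reasons.

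**The case against.** The strongest reply is that the gap is unlikely to be reached in practice.

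- **Timing.** Section 8.2.1 places the loading-dose decision at the move to Part 2. If the SAC decides when it reviews the latest SAD cohort, the highest dose given is the one just reviewed. This stands in part: the unreviewed-dose examples assume a decision made while a higher SAD cohort is in progress. Parallel conduct allows that but does not require it. The point does not touch the declined-dose route.
- **Steady-state rule.** Suppose PK is roughly linear and the loading dose equals the weekly dose times the accumulation ratio R. With a weekly dose of C/k, k between 2 and 3, keeping steady-state exposure within that at C requires R × C/k ≤ C, so R ≤ k. The loading dose is then at most C. This is a fair point, but the protocol does not say how a loading dose is calculated, and Section 6.2 raises target-mediated disposition. On the same assumptions, a ceiling at C would not rule out any such loading dose.
- **SAC judgement.** The SAC authorises each SAD dose beforehand, judges it afterwards, sets the loading dose on safety data and may add MAD sentinels. It is unlikely to choose knowingly a dose it has refused. This stands and is why the practical severity is low. It shows that the committee would probably supply the restraint that the written limit omits.
- **The 2-3 fold rule might already bind loading doses.** The separate ceiling in Section 8.2.1 would then have no purpose, and the protocol does not say so.

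**Conclusion.** The concern holds. As written, the loading-dose ceiling does not exclude a SAD dose that is unreviewed or was declined. It can stand 2-fold above the highest cleared dose on the anticipated doses, and 3-fold above it if the SAC uses the largest permitted step. The µg figures rest on anticipated doses, which the SAC may change, and the overlap examples rest on an assumed cohort schedule.

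This is a defect in a stated safety limit, not permission to give an uncleared dose. A loading dose is optional, and the SAC must justify it on safety data. It is worth correcting but does not threaten the trial.

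**What to change.** In Section 8.2.1, cap the loading dose at the highest SAD cohort dose that the SAC has deemed safe when the MAD cohort starts. This matches the criterion that Section 8.2.2 already uses for the weekly dose. Leave the 2-3 fold rule unchanged.

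In the examples the ceiling falls from 6300 to 3150 µg, from 12600 to 6300 µg, and from 9450 to 3150 µg.

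The cost is one phrase. No procedure is added, since the SAC already decides and documents which SAD doses it considers safe. Any submission to the FDA and IRB under Section 16.1 could go with the next amendment.

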### 8.2.2 Criteria for Dose Decision

Progression to the next dose group will be permitted after review of defined safety and tolerability data suggests that it is safe to do so. All SAC decisions will be documented and signed by the investigator and Sponsor medical monitor or delegate. Evidence of the decision will be retained in the Trial Master File (TMF).

For dose escalation in the SAD phase to proceed data must be available from a minimum of 6 subjects who have completed the planned safety and tolerability assessments out to 96 hours post-dose (Day 5), to ensure at least 4 subjects receive active IMP. For dose escalation in the MAD phase to proceed data must be available from a minimum of 8 subjects who have completed the planned safety and tolerability assessments out to 96 hours post-final dose (Day 26) to ensure at least 6 subjects receive active IMP.

It is planned that the dose will be escalated for each subsequent cohort; however, the SAC may also agree to enroll additional subjects for an intermediate dose level if warranted or may agree to reduce the dose with no limit on the possible extent of reduction. Any decision to investigate an intermediate or reduced dose level will be fully documented.

The decision to proceed to the next dose level will be based on safety and tolerability and data. The following data are required:

- AEs
- Vital signs
- Safety laboratory, including review of PD hematology parameters outlined in [Section 6.4](#)

- 12-lead ECG
- Physical examinations

The SAC may also consider additional data as it becomes available and as relevant to decisions, including ADA, PD, and PK.

Rules for dose decision are as follows:

- Dose escalation will not be more than 3-fold between SAD cohorts. Anticipated SAD dose levels are described in [Table 2](#).
- Dose escalation will not be more than 3-fold between MAD cohorts.
- Dosing for each MAD cohort will be at a dose level 2-3 fold lower than the highest SAD cohort dose deemed safe by the SAC at the time of each MAD cohort initiation.
- Doses administered will be predicted not to exceed a mean  $C_{max}$  of 103,950 ng/mL and a mean  $AUC_{(0-24h)}$  of 1,775,000 ng.h/mL, which is the sex-averaged mean NOAEL exposure limits after the first dose of 18 mg/kg in the cynomolgus NOAEL 28-day good laboratory practice (GLP) toxicology study, in any individual subject.
- The predicted mean steady state exposures in the MAD ( $C_{max}$  and  $AUC$ ) factoring the potential for accumulation will not be anticipated to exceed mean maximal exposures observed in the SAD that were confirmed to be safe and well tolerated.
- The maximum PDM608 dose administered in either part of this trial will not exceed a dose that is more than two-fold above the dose at which any two of the following three pharmacodynamic activities are observed in a sample that includes a minimum 5 of 6 PDM608-treated subjects in SAD or 7 of 9 PDM608-treated subjects in MAD, treated within the same cohort, and observed at any laboratory timepoint up to and including 96 hours post-dose (SAD) and post-final dose (MAD):
  - An increase in mean WBC from pre-dose baseline by  $\geq 3$ -fold
  - An increase in mean monocytes from pre-dose baseline by  $\geq 2$ -fold
  - An increase in mean eosinophils from pre-dose baseline by  $\geq 7$ -fold
- The study will be halted and further dose decisions will be paused:
  - One or more subjects experience a possibly IMP-related serious adverse event (SAE)
  - Two or more subjects experience a possibly IMP-related non-serious AE of severe severity in one cohort in the same organ system class

The decision to reinitiate dosing will be made by the Sponsor in consultation with the investigator after review of safety data and notification to the Institutional Review Board (IRB).

If, following review by the SAC, it is deemed acceptable to continue dose escalation above a defined exposure limit, a substantial amendment with relevant data will be submitted for approval to the regulatory authorities and IRB.

---

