The maximum PDM608 dose administered in either part of this trial will not exceed a dose that is more than two-fold above the dose at which any two of the following three pharmacodynamic activities are observed in a sample that includes a minimum 5 of 6 PDM608-treated subjects in SAD or 7 of 9 PDM608-treated subjects in MAD, treated within the same cohort, and observed at any laboratory timepoint up to and including 96 hours post-dose (SAD) and post-final dose (MAD):

- An increase in mean WBC from pre-dose baseline by  $\geq$  3-fold
- An increase in mean monocytes from pre-dose baseline by  $\geq$  2-fold
- An increase in mean eosinophils from pre-dose baseline by  $\geq$  7-fold

The above three hematologic parameters will be described and made available for review by the SAC when making dose level decisions.

Intra-subject changes are considered because of the wide-variability of hematological parameters between subjects, and because smaller numbers of subjects are allocated to placebo treatment. Multiple pharmacodynamic endpoints are selected to minimize the impact of outliers on mean values. A statistical test is not applied to these pharmacodynamic effects. Dose escalation beyond this point (as described above) is permitted in order to obtain pharmacokinetic and pharmacodynamic margin for subsequent patient studies. This pharmacodynamic limit assumes that PDM608 remains safe as defined by the other stopping rules in [Section 8.5](#).

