## 8.8 Subject Selection List and Randomization

This is a double-blind, randomized, placebo-controlled study; therefore, a randomization schedule will be produced for each study part.

A subject selection list will be produced for each study part prior to dosing using the randomization schedule and will be retained in the Investigative Site File (ISF).

In Part 1, for sentinel dosing, a group of 2 subjects will be dosed ahead of the remaining subjects in each cohort. A randomization schedule will be used such that the first 2 subject numbers will be allocated to active or placebo in a 1:1 ratio (i.e., 1 subject will be randomly assigned to receive PDM608 and 1 subject will be randomly assigned to receive matching placebo). The remaining 6 subject numbers will be allocated to active or placebo in a 5:1 ratio (i.e., 5 subjects will be randomly assigned to receive PDM608 and 1 subject will be randomly assigned to receive matching placebo).

For Part 2, a randomization schedule will be used to allocate subject numbers to PDM608 or placebo in a 3:1 ratio (i.e., in each cohort, 9 subjects will be randomly assigned to receive PDM608 and 3 subjects will be randomly assigned to receive matching placebo).

Subjects will be randomized prior to administration of the first dose.

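### Section 8.2.2 says 8 MAD completers ensure at least 6 subjects on active drug; with 9:3 allocation they ensure only 5

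*Combined protocol and SAP*

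**What the plan says.** Section 8.2.2 sets a data minimum for each escalation decision. In MAD the minimum is 8 subjects, each having "completed the planned safety and tolerability assessments out to 96 hours post-final dose (Day 26) to ensure at least 6 subjects receive active IMP". The sentence before it sets the SAD minimum at 6 subjects with assessments through 96 hours after dosing, "to ensure at least 4 subjects receive active IMP".

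The allocation within cohorts is fixed:
- Section 8.1.1 (SAD): "Within each cohort, 6 subjects will be randomly assigned to receive PDM608 and 2 subjects will be randomly assigned to receive matching placebo".
- Section 8.1.2 (MAD): "Within each cohort, 9 subjects will be randomly assigned to receive PDM608 and 3 subjects will be randomly assigned to receive matching placebo". Section 8.8 repeats this as the 3:1 schedule.

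Section 8.4 allows up to 3 replacements per MAD cohort, but none for a subject withdrawn because of an IMP-related adverse event. Under Section 8.8.1 a replacement receives the regimen of the subject replaced.

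One other rule uses a count of active subjects. The pharmacodynamic dose cap in Sections 6.4 and 8.2.2 counts a trigger only when it is "observed in a sample that includes a minimum 5 of 6 PDM608-treated subjects in SAD or 7 of 9 PDM608-treated subjects in MAD".

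**The concern.** The sentence gives a number of completers and the number of active subjects which that is meant to secure. In a cohort with 3 placebo subjects, the second number does not follow from the first. The SAD sentence uses the same construction and is right, so the word for ensuring is evidently meant as a guaranteed minimum and the MAD figure looks like a slip.

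At stake is what the safety advisory committee can assume about active exposure when it approves the next dose in a first-in-human trial. Under Sections 8.2 and 8.8.2 the committee includes the Sponsor and the investigator, both blinded by default. Unless someone looks at assignments, the completer count is the stated assurance of how many treated subjects support the decision, and in MAD it promises one too many.

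**Working it through.** **Inputs**
- SAD: 6 active, 2 placebo; escalation minimum 6 completers; stated guarantee 4 active (Sections 8.1.1, 8.2.2).
- MAD: 9 active, 3 placebo; escalation minimum 8 completers; stated guarantee 6 active (Sections 8.1.2, 8.8, 8.2.2).

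**Formula.** The fewest active subjects occur when every placebo subject completes:
guaranteed active = completers - placebo subjects in the cohort.

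**Reproducing the plan's figures**
- SAD: 6 - 2 = 4. This matches the stated 4.
- MAD: 8 - 3 = 5. This does not match the stated 6.
- To guarantee 6 in MAD: 6 + 3 = 9 completers.

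Two calculations do give 6, but neither is a minimum for a 9:3 cohort. The average number of active subjects among 8 completers is 8 x 9/12 = 6. Using the SAD placebo count gives 8 - 2 = 6. The documents do not say whether either was used.

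Replacement does not change the bound. Replacements keep the original regimen, so 3 placebo completers remain possible.

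**How often 8 completers include only 5 active.** Assume that the 8 completers are a random subset of the 12, with loss unrelated to arm and no replacements. The number of possible sets is C(12,8) = 495.

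| Active among 8 completers | Sets | Share |
|---|---|---|
| 5 | C(9,5) x C(3,3) = 126 | 25.5% |
| 6 | C(9,6) x C(3,2) = 252 | 50.9% |
| 7 | C(9,7) x C(3,1) = 108 | 21.8% |
| 8 | C(9,8) x C(3,0) = 9 | 1.8% |

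The counts sum to 495. The share below the stated 6 is 126/495, or 25%. With 9 completers it is 0, because 9 - 3 = 6. These shares are conditional on the number of completers.

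**Comparison with the cap's sample floor.** The escalation minimums guarantee 4 active completers in SAD against a floor of 5, and 5 in MAD against a floor of 7. A cohort can therefore qualify for escalation with fewer active completers than the floor. The two rules count different things, however (see the objection), so no percentage is attached to this.

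**The case against.** The best defence is that little depends on the difference. Having only 5 active completers among 8 requires all four non-completers to come from the active arm. No power statement or analysis rule uses 6 rather than 5, and SAD escalation is accepted on 4. The committee is also not confined to the completer count: Section 8.8.2 allows access to assignments if warranted at scheduled safety reviews, and allows individual data to be shown where needed for dose selection. All of this stands, and it is why the point is minor. It does not make the sentence true. The defence that 6 is the expected number also fails, because an average guarantees nothing and the SAD sentence is a true worst case.

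A reader might infer more: that the pharmacodynamic cap fails whenever a cohort escalates with fewer than 5 (SAD) or 7 (MAD) active completers. The documents do not support that.
- Both sections that state the cap set its minimum sample explicitly, and Section 6.4 says there is concern about outliers moving the means. A floor fits that concern and reads as deliberate.
- The escalation minimum counts subjects who completed the planned assessments. The cap uses hematology at any timepoint up to 96 hours. A subject who missed only an ECG, or who left after some draws, can still count at the draws taken. SAD subjects are resident through Day 8.
- Section 8.2.2 makes review of the three hematology parameters mandatory at each decision and lets the committee choose a lower or intermediate dose. The halting rules apply regardless.

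What remains is a silence: no section says what the committee does when the escalation minimum is met but the cap's floor is not. A reader might equally dismiss this for MAD because doses are set "at a dose level 2-3 fold lower than the highest SAD cohort dose deemed safe by the SAC". That goes too far as well, since Section 8.2.1 permits a MAD loading dose up to the highest SAD dose.

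**Conclusion.** Wrong as written; minor severity. With 9 active and 3 placebo subjects per MAD cohort, 8 completers guarantee 5 active, not 6. This is exact and needs no assumption beyond the stated allocation and the same-regimen replacement rule. The SAD figure is correct.

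The 25% applies only to cohorts with exactly 8 completers and assumes that loss is unrelated to arm and that no replacements are made. Loss concentrated in the active arm would raise it. With no loss rate in the documents, the frequency of such cohorts is not estimated.

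The documents do not show whether 6 active was the intended requirement or only a miscalculated consequence of requiring 8, so the choice of correction is the sponsor's. The relation between the escalation minimums and the cap's floor is an optional clarification, not an error.

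**What to change.** In Section 8.2.2, do one of the following:
- Keep 8 completers and restate the guaranteed number on active drug as 5. This is a wording change only, with no new procedure and no change in cohort size.
- If 6 active is the intended minimum, require 9 completers, or require at least 6 active completers confirmed by unblinded staff. The cost is that an escalation may have to wait for a replacement. Requiring 9 would also mean aligning the target of 8 evaluable MAD subjects in the synopsis and Section 14.1.

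Optionally, add a sentence to Sections 6.4 and 8.2.2 saying what the committee does when a cohort meets the escalation minimum but fewer active subjects than the cap's floor have hematology. Lowering or removing the floor would be a design choice, not a correction: it changes when a dose-limiting rule applies and leaves the mean more exposed to outliers.
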